5. STATISTICAL ANALYSES

5.1. General Considerations

5.1.1. Study Phases

A baseline (or reference) value will be defined as the value of the last available assessment prior to the first vaccination on Day 1, unless specified otherwise. The safety analysis will present all results by phase (see Section 5.2).

Immunogenicity results will be presented per scheduled time point as appropriate using visit windows (see section 1.4 in the protocol). Listings will be presented per phase and time point.

Study day or relative day is defined as follows:

Study Day = visit date - date of Day 1 + 1; if visit date \geq date of Day 1 (date of first vaccination).

Study Day = visit date - date of Day 1; if visit date $<$ date of Day 1 (date of first vaccination).

Relative day (relday), the number of days in the analysis time point will be defined as:

relday = visit date - reference date + 1 for visits on or after the reference date,

relday = visit date - reference date for visits before the reference,

where the reference date equals the date of vaccination 1 or 2.

The planned primary and final analysis will be performed on unblinded data. During primary analysis data will be unblinded to the sponsor.

5.1.2. Phase Definitions

The phases in the study will be constructed, as follows in [Table 5](#)

Table 5: Phase Definitions

Phase	Phase #	Period	Period #	Interval	
				From	To
Screening	1			Date and time of signing the informed consent form	One minute prior to start of post dose 1 period
Post-dose	2	Post-dose 1	1	Date and time of first vaccination	Minimum of: a) 23:59 at the date of last contact (for early discontinuation) b) One minute prior to the date of unblinding visit or database cut-off date, whichever occurs first c) 23:59 on 28 days after the first vaccination (23:59 of day of vaccination + 28 days)
Follow-up 1	3			One minute after post-dose 1 period end	Minimum of: a) 23:59 at the date of last contact (for early discontinuation) b) One minute prior to the date of unblinding visit or database cut-off date, whichever occurs first c) One minute prior to date and time of second vaccination
Post-dose	2	Post-dose 2	2	Date and time of second vaccination	Minimum of: a) 23:59 at the date of last contact (for early discontinuation) b) One minute prior to the date of unblinding visit or database cut-off date, whichever occurs first c) 23:59 28 days after the second vaccination (23:59 of day of vaccination + 28 days)
Follow-up 2	4			One minute after post-dose 2 period end	Minimum of: a) 23:59 at the date of last contact (for early discontinuation) b) One minute prior to the date of unblinding visit or database cut-off date whichever occurs first

					c) One minute prior to 6 months after second vaccination
Follow-up 3	5			One minute after post-dose 2 period end	
Minimum of:
 
a) 23:59 at the date of last contact (for early discontinuation)
 
b) One minute prior to the date of unblinding visit or database cut-off date, whichever occurs first
 
c) 23:59 at the date of last visit

Note: the end of regimen phase should be the end of the last post dose period

FU3: Full follow-up from end of post dose 2 to end of study or last contact

Post-dose 1 and post dose 2 Combined includes events occurring in the post-dose 1 and/or post dose 2 phases (not including FU 1 or FU2 or FU3)

For final analysis the following criteria for Follow-Up 3 will be used 23:59 at date of last contact (for early discontinuation or date of last visit)

5.1.3. Visit Windows

Per-protocol visit windows (refer to CTP section 1.4) guide study procedures. Analysis visit windows are defined considering the emerging data from other studies relating to sampling time points and potential impact on immunogenicity. As such, analysis windows may be redefined prior to unblinding. No time windows apply for Early Exit visit sampling.

The following visit window rules will be considered for the analysis of immunogenicity results:

For vaccination:

1. If a participant missed a scheduled vaccination, all immunogenicity samples taken after the missed vaccination will be excluded from the PPI. Samples taken before will still be included in the PPI.
2. If the scheduled vaccination at vaccination visit Day 57 is $\geq -9/+16$ days from planned vaccination date (outside Day 49- Day 72), all immunogenicity samples taken after will be excluded from the PPI. I.e., if the vaccine is administered at least 9 days before or at least 16 days after the planned vaccination date, all immunogenicity samples taken on or after will be excluded from the PPI set.

For immunogenicity sampling (excluding D2, D4, D8, D58, D60 and D64 for sub-study participants):

1. If immunogenicity sample is taken out of window when planned within three months (≤ 3 months) post dose 1 vaccination (i.e. up to and including Day 71 visit), the sample will be excluded from PPI as follows:
 - a. For sampling at D29 if taken $\geq -/+9$ days from the planned Visit date.
 - b. For sampling at D57 if taken $\geq -9/+16$ days from the planned Visit date.
 - c. For sampling at D71 if taken $\geq -4/+16$ days from the planned Visit date.

For example, samples outside the following windows will be excluded:

- a) Post Vac 1 + 28-day visit (D29): samples taken outside 21 days and up to 37 days post vaccination 1 will be excluded.

b) Vac 2 visit (D57): samples taken outside 49 days and up to 72 days post vaccination 1 will be excluded.

c) Post Vac 2 + 14 day visit (D71): samples taken outside 11 days and up to 29 days post vaccination 2 will be excluded.

d) Other samples from these participants can still be included in PPI.

2. If immunogenicity sample is taken out of window when planned 24 weeks post last vaccination and thereafter, this sample will be excluded from PPI if taken $\geq/-/+ 30$ days from Visit timing date. Other samples from this participant can still be included in PPI.

For early immunogenicity sampling in the sub-study (includes only D2, D4, D8, D58, D60 and D64 for sub study participants): If immunogenicity sample is taken outside of the protocol-defined windows as defined in CTP 1.4.2 schedule of activities, these samples will be excluded from the PPI.

5.1.4. Pooling Algorithm for Analysis Centers

Data will be pooled across the different centers.

5.1.5. Definition of Subgroups

The following subgroups will be investigated for immunogenicity: Sex, Age group, SARS-CoV-2 Serostatus at baseline and race. For selected safety and immunogenicity assessments, subgroup analysis will include age group, serostatus and BMI. Sub-group analysis for serostatus at baseline will only be done if at least ~10% of participants are seropositive at baseline. Final analysis for immunogenicity may include subgroups analyses for SARS-CoV-2 infection during the study and for off-study COVID-19 vaccination.

Subgroup	Definition
BMI	
 underweight $<18.5 \text{ kg/m}^2$ normal $18.5-25 \text{ kg/m}^2$ overweight $25-30 \text{ kg/m}^2$ obese $\geq 30 \text{ kg/m}^2$
Age Group 1	
 18-40 41-55
Age Group 2	
 18-25 26-40 41-55
Ethnicity	
 Hispanic or Latino, Not Hispanic or Latino, Not Reported Unknown
Sex	
 Male Female Intersex Unknown
Race ^a	
 American Indian or Alaska Native Asian Black or African American

Subgroup	Definition
	
 Native Hawaiian or other Pacific Islander White Not reported Unknown
SARS-CoV-2 Serostatus ^b at baseline	
 Positive Negative Missing
SARS-CoV-2 infection ^c during study	
 Yes No
Off-study COVID-19 vaccination during the study	
 Yes No

^aIf multiple race categories are indicated, the Race is recorded as 'Multiple'

^bSerostatus at baseline will be based on central testing, namely S and/or non-Spike-based serology (e.g. N-ELISA or equivalent assay, such as the Roche Elecsys anti-SARS-CoV-2 assay), as available, and is defined as:

- Positive for participants who are positive at baseline by S-ELISA, and/or non-S-based serology (e.g. N-ELISA or equivalent assay, such as the Roche Elecsys anti-SARS-CoV-2 assay), as available.
- Negative for participants who are negative at baseline by S-ELISA, and non-S-based serology (e.g. N-ELISA or equivalent assay, such as the Roche Elecsys anti-SARS-CoV-2 assay), if available.
- Missing if data on all of the above assays are missing, or if one of the assays is missing and the other is negative.

^cSARS-CoV-2 infection is defined as a positive SARS-CoV-2 PCR test or conversion from a negative at baseline to positive post-baseline result with a non-Spike protein-based serology test (e.g. N serology).

Additional subgroup analyses might be performed for safety or immunogenicity if it is deemed useful to the study objectives.

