- e. For those participants who are unable to continue participation in the study up to Visit 7, but for whom consent is not withdrawn, an early exit visit will be conducted as soon as possible. Participants who wish to withdraw consent from participation in the study will be offered an optional visit for safety follow-up. This includes the safety assessments of the early exit visit (no blood sampling for immunogenicity). If the participant does not want to receive the second vaccination, they can continue with other study procedures.
- f. Signing of the ICF should be done before any study-related activity.
- g. A history-directed physical examination, including height and body weight, will be carried out at screening. At other visits, an abbreviated, symptom-directed examination will be performed if determined necessary by the investigator.
- h. Heart rate, systolic and diastolic blood pressure, respiratory rate, and body temperature. Heart rate and blood pressure measurements should be taken in the supine position and preceded by at least 5 minutes of rest. Vital signs measurements are recommended before blood sampling. Body temperatures will be measured preferably via the oral route.
- i. The blood draw at screening will be used to determine serostatus by serological testing for eligibility in the main and sub study by a local laboratory.
- j. Investigator must check for acute illness or body temperature $\geq 38.0^{\circ}\text{C}/100.4^{\circ}\text{F}$ at the time of vaccination. If any of these events occur within 24 hours prior to planned vaccination, the vaccination can be rescheduled as long as this is in agreement with the allowed windows. If the vaccination visit cannot be rescheduled within the allowed window or the contraindications to vaccination persist, the sponsor should be contacted for further guidance. The investigator should also check if any other reasons, as listed in Section 7.1, Discontinuation of Study Vaccination, have been met and would prevent further study vaccination.
- k. For women of childbearing potential only.
- l. Serum collected can also be used for N-serology testing.

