A target of approximately 240 participants will be enrolled in the sub study and will receive a 2-dose vaccination regimen at either 9×10^{10} vp, 5×10^{10} vp, 2.5×10^{10} vp, or 1.25×10^{10} vp. This target may not be met due to the challenges of enrolling seronegative subjects into the study, so sub-study enrollment may stop at lower numbers.

Table 2: Schematic Overview of Study Design and Groups for the Sub Study

Group	N (Seronegative)*	N (Seropositive)	Day 1 Vaccination 1	Day 57 Vaccination 2
1	~ 40	~ 20	Ad26.COV2.S 9×10^{10} vp	Ad26.COV2.S 9×10^{10} vp
3	~ 40	~ 20	Ad26.COV2.S 5×10^{10} vp	Ad26.COV2.S 5×10^{10} vp
5	~ 40	~ 20	Ad26.COV2.S 2.5×10^{10} vp	Ad26.COV2.S 2.5×10^{10} vp
6	~ 40	~ 20	Ad26.COV2.S 1.25×10^{10} vp	Ad26.COV2.S 1.25×10^{10} vp

*Due to the challenges of enrolling seronegative subjects into the study, study enrollment may stop at lower numbers.

Table 3: Humoral Immunity Blood Sampling Schedule in Participants in All Groups of the Main and Sub Study

Groups**		Month 1	Month 2	Month 3	Month 6*	
	Day 1	Day 29	Day 57	Day 71		
1 6	●	●	●	●	●	

*post last vaccination

**Groups 1, 3, 5 and 6 in the sub study

Table 4: SARS-CoV-2 Non-S Serology Schedule in Participants in All Groups of the Main and Sub Study

Groups**		Month 1	Month 2	Month 3	Month 6*	
	Day 1	Day 29	Day 57	Day 71		
1 6		●		●		

*post last vaccination

** Groups 1, 3, 5 and 6 in the sub study

Table 5: Serum Sampling and PaxGene Schedule for Innate MoA in Participants in Groups 1, 3, 5 and 6 of the Sub Study

Groups	Day 1*	Day 2	Day 4	Day 8	Day 57*	Day 58	Day 60	Day 64
1, 3, 5 and 6	●	●	●	●	●	●	●	●

*pre vaccination

MoA=mechanism of Action

An IDMC has been commissioned for the Ad26.COV2.S program. Any significant safety information will be shared with the IDMC. Refer to Committees Structure in Section 10.3, for details.

A diagram of the study design is provided in Section 1.2, Schema.

Study Duration

The study duration from screening until the last follow-up visit will be at least 8 months per participant. The study will consist of a 28-day screening phase with vaccinations on Day 1 and Day 57, and a follow-up of at least 6 months after the last vaccination.

The vaccination phase consists of the administration of 1-dose of Ad26.COV2.S on Day 1 and 1-dose of Ad26.COV2.S on Day 57. A follow-up of at least 6 months after vaccination 2, is foreseen.

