4. POPULATIONS (ANALYSIS SETS) FOR ANALYSIS

For vaccine studies, study intervention assignment will follow the as treated principle: all analyses (including safety, immunogenicity) will be analyzed by the received vaccine.

Analysis Sets	Description
All screened participants (ALL)	The “all screened participants” set includes all participants that were screened, regardless of whether they were enrolled and/or randomized.
All randomized participants (ALL RANDOMIZED)	The “all randomized participants” set includes all participants that were randomized to one of the treatment groups.
Full Analyses Set (FAS)	The Full Analysis Set will include all participants with at least one vaccine administration documented
Per Protocol Immunogenicity Set (PPI)	The Per Protocol Immunogenicity population will include all randomized and vaccinated participants for whom immunogenicity data are available excluding participants with major protocol deviations expected to impact the immunogenicity outcomes (see section 4.1). In addition, samples obtained after missed vaccinations or samples obtained from participants after SARS-CoV-2 infection occurring after screening (if applicable) will be excluded from the analysis set (see below section 4.1).
NI Analysis Set	The NI analysis set will include all PPI participants who are SARS-CoV-2 seronegative at study entry ^a .

^a SARS-CoV-2 seronegative as assessed by central testing (based on S- and/or N- serology at baseline)

NB. As detailed in Section 4, formal non-inferiority hypothesis testing will be performed on either the NI set or on the PPI set under different scenarios (Scenario 1 or Scenario 2, respectively).

Further details on the selection of PPI and NI set are described below.

The safety and reactogenicity analyses will be censored at the date of unblinding or the receipt of an unscheduled vaccine, whichever event occurs first. AEs reported after unblinding or receipt of an unscheduled vaccine, whichever comes first, will be listed.

The immunogenicity analyses will be censored at the date of the receipt of an unscheduled vaccine. Immunogenicity samples taken after the receipt of an unscheduled vaccine will be included in the listings and flagged.

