4.1. Selection of PPI dataset

- Samples obtained from participants after SARS-CoV-2 infection occurring after screening (if applicable) will be excluded from the analysis set.
 - This includes COVID-19 cases with a positive RT-PCR or molecular test, but also participants who develop a post-baseline positive result in non-S-based serology (e.g. N-ELISA or equivalent assay, such as the Roche Elecsys anti-SARS-CoV-2 assay) if the test was negative at baseline. Samples at the time of positive RT-PCR or molecular test, or non-S-based serology and thereafter will be excluded from PPI.
 - Participants with missing or having undetermined SARS-CoV-2 serostatus at baseline will be excluded from PPI.
- Major Protocol Deviations (MPDs) with impact on immunogenicity will be considered for the PPI population. MPDs are defined in the MPD Criteria document. Different rules are applicable for selected MPDs with impact on immunogenicity:
 - For MPDs with impact on immunogenicity which concern inclusion or exclusion criteria (category: entered but did not satisfy criteria), the whole subject will be excluded from PPI.
 - For MPDs with impact on immunogenicity which can affect immunogenicity outcomes from the time of PD and thereafter, such as missed vaccinations, out of window vaccinations (Day 57 visit), use of disallowed concomitant medications or off-study COVID-19 vaccines (categories: received a disallowed concomitant treatment, received wrong treatment or incorrect dose, developed withdrawal criteria but no withdrawn, in addition to ‘missed vaccination’ under the category ‘Other’, and ‘received vaccination outside of visit window’ under the category ‘Dosage & Administration’), any samples obtained at the time of PD and thereafter will be excluded from PPI. Samples taken from the subject prior to such PDs can be included in PPI.
 - For MPDs with impact on immunogenicity which can affect immunogenicity outcomes only at the time of PD, such as out of window visits or blood collections (category: Other except for missed vaccination or out of window vaccinations which is included in the rule above), samples obtained at the time of PD will be excluded from PPI only. Samples taken from the subject prior to or after such PDs can be included in PPI.
 - The exact PD rules may be amended, or other PD types may be added, this will be further described in the DPS. For PDs relating to out of window visits or sampling, the windows will be defined as indicated in Section 5.1.3.

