Adenovirus 26 neutralization will be measured in a subset of participants at Day 1 and at Day 57 to assess the impact of pre-existing Ad26 neutralizing antibodies in humoral immunogenicity against SARS-CoV-2 (S-ELISA, psVNA including emerging variants and/or wtVNA). Ad26 VNA sample values >LOD are considered positive.

Descriptive statistics (N, geometric mean and corresponding 95% CI, number, and percentage of positive samples) will be calculated. Spearman correlation between Ad26 VNA at Day 1 (if sufficient number of Ad26-seropositive participants) or Day 57 and S-ELISA concentrations or psVNA including emerging variants or wtVNA titers at Day 29 or Day 71, respectively, will be calculated and visualized with a scatterplot.

Scatterplots between humoral assay results will be provided for selected time points. These may include but are not limited to:

Binding antibodies (S-ELISA) versus wild type VNA

Binding antibodies (S-ELISA) versus pseudo-virion expressing S protein VNA (including emerging variants)

Wild type VNA versus pseudo-virion expressing S protein VNA

Ad26 VNA versus binding antibodies (S-ELISA)

Ad26 VNA versus wild-type VNA

Ad26 VNA versus pseudo-virion expressing S protein VNA (including emerging variants)

If a similar assay is performed at different analyzing labs, then the statistical analyses may distinguish between these and provide separate scatterplots for each analyzing lab versus the other assay of interest. These scatterplots will display the values as analyzed for the geometric mean calculations. Spearman's rank correlation coefficients will also be provided (one per scatterplot).

Further details and/or updated rules will be provided in the DPS.

Definition of SARS-CoV-2 infections

A SARS-CoV-2 infection is defined as a participant with:

- serologic conversion between baseline (Day 1; pre-vaccination) and selected timepoints post-vaccination using an ELISA and/or SARS-CoV-2 immunoglobulin assay that is dependent on the SARS-CoV-2 N protein (e.g., N-ELISA or equivalent assay, such as the Roche Elecsys anti-SARS-CoV-2 assay), for participants that are N serology negative at baseline, or
- reported positive SARS-CoV-2 PCR test during the study.

For participants with missing N serology result at baseline, a post baseline positive N serology result will not be considered a COVID-19 infection.

Assessment of occurrence of asymptomatic SARS-CoV-2 infection

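### A participant who is S-ELISA negative with no baseline N result is both Negative and Missing in the SAP; the choice decides NI-set membership, retention of infections seen only by N serology, and possibly the primary scenario

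*SAP*

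**What the plan says.** Baseline serostatus is defined in footnote b of SAP 5.1.5 and repeated under the demographics table in SAP 5.2.1.

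- Negative: "Negative for participants who are negative at baseline by S-ELISA, and non-S-based serology", with the N requirement qualified at the end: "such as the Roche Elecsys anti-SARS-CoV-2 assay), if available". SAP 5.2.1 uses *as available* instead.
- Missing: "Missing if data on all of the above assays are missing, or if one of the assays is missing and the other is negative".

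Neither section says which rule prevails. Four other places depend on the label:

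- SAP Section 4, footnote to the NI analysis set: "SARS-CoV-2 seronegative as assessed by central testing (based on S- and/or N- serology at baseline".
- SAP 4.1: "Participants with missing or having undetermined SARS-CoV-2 serostatus at baseline will be excluded from PPI". The NI set is a subset of PPI, so these participants leave both.
- SAP 6.1.4, definition of infection: "For participants with missing N serology result at baseline, a post baseline positive N serology result will not be considered a COVID-19 infection". SAP 4.1 and the end of 6.1.4 likewise remove samples after a positive N result only when the baseline N result was negative. A positive PCR counts as infection whatever the baseline N result.
- SAP 4.2 states that data following infection during the study are left out of the non-inferiority assessment. It also moves the primary analysis to Scenario 2 if more than 40% of evaluable data points in the NI set are lost at Day 29.

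On whether a baseline N result will exist, Protocol Table 4 ("SARS-CoV-2 Non-S Serology Schedule in Participants in All Groups of the Main and Sub Study") and the schedules in Protocol 1.4 mark central N draws at Day 29 and Day 71 only. For the humoral serum, which includes the Day 1 draw, a footnote adds: "Serum collected can also be used for N-serology testing". SAP 6.1.4 nonetheless tabulates N positivity at Day 1 and counts participants whose baseline N result is missing.

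**The concern.** A participant who is S-ELISA negative at baseline and has no baseline N result satisfies both definitions. The and/or in the NI-set footnote favours Negative; SAP 4.1 combined with the Missing definition points the other way. Two programmers could build different primary sets from the same text.

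Under Negative, the participant enters the NI set and a later positive N result triggers nothing. S-ELISA values after an infection seen only by N serology then enter the primary comparison, contrary to the intention in SAP 4.2. If infection raises titres to similar levels whatever the dose, these values pull the GMC ratio towards 1 and favour non-inferiority. That is the error to guard against in a trial meant to support end-expiry specifications.

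Under Missing, that route closes, but every such participant is lost from the NI set and counts towards the 40% trigger.

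**Working it through.** **The plan's own figures.** Inputs from SAP Section 3: SD 0.5 on log10, margin log10(1.5) = 0.1761, one-sided alpha 0.0125, power 90%, true difference 0.

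n = 2 × (2.2414 + 1.2816)² × 0.5² / 0.1761² = 200.1, so 201 evaluable per group. Dividing by 1 − 0.102 gives 224, against 225 stated. The powers in SAP Table 4 also reproduce to within 2 percentage points. The enrolment total in that table is 4 × 265 + 2 × 225 = 1,510, and 40% of it is 604.

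**Inputs for the check.** N-positivity is 27% at Day 29 and 38% at Day 71 (SAP 4.2, blinded look at the main study; applied here to the combined set). Let f be the share with no baseline N result. The documents do not give f, so a range is shown. The following assumptions make the contamination figures upper bounds: every N-positive is a new infection, none is seen by PCR or by baseline S-ELISA, and there are no other losses.

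**Contaminated share of the NI set under Negative.** N-positives with a negative baseline N result are removed; those without one stay. With q the N-positive proportion:

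c = f·q / [f + (1 − f)(1 − q)]

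- Day 29, f = 10%: 0.027 / (0.10 + 0.90 × 0.73) = 3.6%
- Day 29, f = 25%: 0.0675 / (0.25 + 0.75 × 0.73) = 8.5%
- Day 71, f = 10%: 0.038 / (0.10 + 0.90 × 0.62) = 5.8%
- Day 71, f = 20%: 0.076 / (0.20 + 0.80 × 0.62) = 10.9%

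**Type I error at Day 71.** Take two arms of 265 enrolled and a true ratio of exactly 2/3 in uninfected participants. Assume that infected participants have the same mean in both arms, D = 0.5 to 1.0 log10 above the uninfected reference mean. D is an assumption; the documents give no value.

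- n per arm = 265 × [f + (1 − f) × 0.62]
- expected log10 difference = −0.1761 × (1 − c)
- variances: 0.25 + c(1 − c)D² (reference) and 0.25 + c(1 − c)(D + 0.1761)² (test)
- type I error = Φ(0.1761·c / SE − 2.2414), where SE² = (sum of the two variances) / n

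| f | c | n per arm | expected ratio | type I, D = 0.5 | type I, D = 1.0 |
|---|---|---|---|---|---|
| 0 | 0 | – | 0.667 | 0.0125 | 0.0125 |
| 10% | 5.8% | 174 | 0.682 | 0.0198 | 0.0191 |
| 20% | 10.9% | 184 | 0.697 | 0.0290 | 0.0264 |

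**Scenario trigger at Day 29.** Loss under Missing is f + (1 − f) × 0.27; loss under Negative is (1 − f) × 0.27.

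- f = 10%: 34.3% against 24.3%
- f = 20%: 41.6% against 21.6%

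Under Missing the 40% line is crossed once f exceeds 1 − 0.60/0.73 = 17.8%. If 10% are lost for other reasons, it is crossed at 1 − 0.60/(0.90 × 0.73) = 8.7%.

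**The case against.** The strongest reply is that the SAP already has a specific rule for this case. The second clause of the Missing definition has no use unless it covers the S-negative participant without an N result. If the specific rule prevails, SAP 4.1 removes these participants and no contamination arises. The infection rule in SAP 6.1.4 then makes sense, because without a baseline result a past infection cannot be told from a new one. The qualifier in the Negative definition might also mean that the N assay exists for the study, not that the individual has a result. This is probably the intended reading, but the SAP does not say so, and the and/or in the NI-set footnote points the other way.

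Three stronger readings might be inferred, and the documents do not support them.

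- *All infected samples stay under Negative.* They do not: SAP 4.1 and 6.1.4 remove samples from a positive PCR onwards under either label. Only infections seen solely by N serology remain.
- *No one will have a Day 1 N result, so the NI set is either empty or fully contaminated.* The protocol does not schedule a dedicated draw, but SAP 6.1.4 plans to tabulate Day 1 N results and defines conversion from Day 1.
- *The main harm is lost power.* Under Negative the infected participants are retained, so the sample size rises. Bias towards non-inferiority matters more.

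It also stands that some of the 27% and 38% may be baseline positives missed by local tests, as SAP 4.2 notes; central S-ELISA would class many of these as Positive. And if infected participants kept the same dose ratio as uninfected ones, the GMC ratio would not be biased.

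**Conclusion.** The conflict is real as written: one participant, two labels, no precedence, and different handling in the primary analysis. If f is near zero, the effect is negligible. Contamination is at most 3.6% of the NI set at Day 29 for f = 10% and 8.5% for f = 25%. At Day 71 the one-sided type I error per comparison rises from 0.0125 to about 0.02 for f = 10% and to 0.026-0.029 for f = 20%, if infected titres are equal across arms and 0.5 to 1.0 log10 higher. At f = 20% the two labels fall on opposite sides of the 40% trigger. Switching to Scenario 2 does not remove the problem, because under Negative the same participants would enter the PPI model coded as seronegative.

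**What to change.** Before unblinding:

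1. Delete *if available* from the Negative definition in SAP 5.1.5 and *as available* from the one in SAP 5.2.1, so that Negative requires both assays to be negative.
2. Change *and/or* to *and* in the NI-set footnote in SAP Section 4. The Missing definition then governs S-negative participants without an N result, and SAP 4.1 excludes them.
3. State that central N serology is run on the Day 1 serum, and report how many results are missing.

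Leave the infection rule in SAP 6.1.4 as it is. Once the Missing definition governs, a rule excluding samples after a first positive N result when baseline N is missing would act mainly on S-positive participants. Their later positive N result may reflect an earlier infection, and they belong in the Scenario 2 population.

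The cost is a few words in the SAP plus N testing of serum already drawn. The downside is that S-negative participants with no Day 1 N result leave the NI set and count towards the 40% trigger, so completing the Day 1 testing matters.
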